7 STUDY OBJECTIVES

7.1 Primary Objectives

The primary objectives of the study are:

- To assess the clinical efficacy of amifampridine phosphate compared to placebo in subjects with LEMS, based upon improvement in subject global impression (SGI) and quantitative myasthenia gravis (QMG) score; and
- To confirm the safety and tolerability of amifampridine phosphate by adverse event reports.

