8.1 Overall Study Design and Plan

This randomized (1:1), double-blind, placebo-controlled, parallel-group study is designed to evaluate the efficacy and safety of amifampridine phosphate in patients diagnosed with LEMS. Patients will have been receiving unblinded drug treatment in the expanded access program (EAP-001), after which blinded treatment effect will be assessed for continuation or cessation of drug. The study is planned to include approximately 28 male and female patients. The planned duration of participation for each patient is 5 days, excluding the screening period, which can last up to 7 days.

Those patients successfully satisfying all screening criteria will be randomized to a treatment group. Amifampridine phosphate (at the patient's optimal dose) or placebo will be dispensed by the site pharmacist, according to the randomization schedule, to begin with the next dose after all Day 0 assessments are completed and continued for 4 days. After completion of the study, patients will be eligible for expanded access treatment program with open-label amifampridine phosphate. Since patients will have been out of the expanded accesss program for less than 30 days, as LMS-003 participants, rescreening to return to expanded access program will not be required, per the protocol, and patients may immediately resume their participation in the expanded access program (EAP-001).

Page 29

Screening

Patients receiving amifampridine phosphate treatment for LEMS, and meeting the inclusion and exclusion criteria are eligible to participate in this study. They can be randomized if on stable dose and frequency of amifampridine phosphate for at least 1 week before being randomized to a treatment. Screening and randomization (Day 0) may be combined into a single visit.

Treatment (Days 1-4) (+1 day)

Patients will be randomized (1:1 ratio) on the last day of the screening period (Day 0) to either amifampridine phosphate or placebo. Beginning with the next dose after all Day 0 assessments are completed, the patient will take, under double-blind conditions, either amifampridine phosphate tablets or placebo tablets through Day 4, with a clinic visit on the last day (Day 4) for assessments (Table 3). Any unused portion of dispensed drug will be returned to the pharmacy.

During the study, safety and efficacy assessments will be made as detailed in the Schedule of Assessments in Table 3.

Table 3. Schedule of Assessments

	Samaaning	Randomization	Days 1-4

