8.2.1 Inclusion Criteria

Individuals eligible to participate in this study must meet all of the following inclusion criteria:

- 1. Male or female ≥18 years of agewith LEMS and currently receiving a stable dose of amifampridine phosphate for at least 7 days.
- 2. Diagnosis of LEMS by antibody testing or EMG.
- 3. Completion of anti-cancer treatment at least 3 months (90 days) prior to Screening.
- 4. If receiving peripherally acting cholinesterase inhibitors (e.g. pyridostigmine), a stable dose of cholinesterase inhibitors is required for at least 7 days prior to randomization and throughout the study.
- 5. If receiving permitted oral immunosuppressants (prednisone or other corticosteroid,), a stable dose is required for at least 30 days prior to randomization and throughout the study.
- 6. Female patients of childbearing potential must practice effective, reliable contraceptive regimen during the study.
- 7. Able to perform all study procedures and assessments.
- 8. Willing and able to travel to study site and attend all clinic study visits.
- 9. Willing and able to provide written informed consent.

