9 REPORTING ADVERSE EVENTS

9.1 Adverse Events

For this protocol, a reportable AE is any untoward medical occurrence (e.g. sign, symptom, illness, disease or injury) in a patient administered the IP or other protocol-imposed intervention, regardless of attribution. This includes:

- AEs not previously observed in the patient that emerge during the course of the study.
- Pre-existing medical conditions judged by the Investigator to have worsened in severity or frequency or changed in character during the study.
- Complications that occur as a result of non-drug protocol-imposed interventions.

An adverse drug reaction is any AE for which there is a reasonable possibility that the IP caused the AE. "Reasonable possibility" means there is evidence to suggest a causal relationship between the IP and the AE

Whenever possible, it is preferable to record a diagnosis as the AE term rather than a series of terms relating to a diagnosis.

The study period during which all serious and non-serious AEs will be reported begins after informed consent is obtained and through the last visit on Study Day 4, or at the time of early

Page 43

discontinuation. The criteria for determining, and the reporting of SAEs is provided in Section 9.2.

The Investigator should follow all unresolved AEs until the events are resolved or stabilized, the patient is lost to follow-up, or it has been determined that the study treatment or participation is not the cause of the AE. Resolution of AEs (with dates) should be documented on the appropriate CRF page(s) and in the patient's medical record.

The Investigator responsible for the care of the patient or qualified designee will assess AEs for severity, relationship to IP, and seriousness (refer to Section 9.2 for SAE definition). Severity (as in mild, moderate or severe headache) is not equivalent to seriousness, which is based on patient/event outcome or action criteria usually associated with events that pose a threat to a patient's life or functioning. Seriousness (not severity) serves as a guide for defining regulatory reporting obligations.

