The Investigator will determine the severity of each AE using the following Common Terminology Criteria for Adverse Events (CTCAE v4) grades defined in Table 5 (the event will be recorded on the source documents and AE CRF). Events that are CTCAE grades 4 and 5 are serious events and require completion of both an SAE form and AE CRF. Adverse events that do not have a corresponding CTCAE term will be assessed according to the general guidelines for grading used in the CTCAE as stated below.

Page 44

Table 5. Categories of Severity for CTCAE Criteria

Severity	Description		
Grade 1	Mild; asymptomatic or mild symptoms; clinical or diagnostic observations only; intervention not indicated.		
Grade 2	Moderate; minimal, local or noninvasive intervention indicated; limiting age-appropriate instrumental ADL*.		
Grade 3	Severe or medically significant but not immediately life-threatening; hospitalization or prolongation of hospitalization indicated; disabling; limiting self care ADL**.		
Grade 4	Life-threatening consequences; urgent intervention indicated.	Note: Grade 4 and 5 adverse events should	
Grade 5	Death related to AE.	always be reported as serious adverse events	

Activities of Daily Living (ADL)

The Investigator will suggest the relationship of an AE to the IP and will record it on the source documents and AE CRF, using the relationship categories defined in Table 6.

The Investigator should review the AE Log for the patient, from the EAP-001 expanded access program. Any ongoing/open/unresolved AEs will be transcribed to the LMS-003 study AE Log. At the end of patient's participation in the LMS-003 study, the AE Log should be provided to the expanded access program site, so that the expanded access site can update their AE Log with any changes.

^{*} Instrumental ADL refer to preparing meals, shopping for groceries or clothes, using the telephone, managing money, etc.

^{**}Self care ADL refer to bathing, dressing and undressing, feeding self, using the toilet, taking medications, and not bedridden.

Page 45

Table 6. Description of Relationship to Adverse Event Categories

Relationship Category	Description
Not Related	Exposure to the IP has not occurred OR The administration of the IP and the occurrence of the AE are not reasonably related in time OR The AE is considered likely to be related to an etiology other
	than the use of the IP; that is, there are no facts [evidence] or arguments to suggest a causal relationship to the IP.

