13.3 Safety Analysis

Safety analyses will be conducted on the Safety Population. The safety analysis will be descriptive and will be presented using observed data only.

All AEs will be coded using the Medical Dictionary for Regulatory Activities (MedDRA). Only TEAEs will be included in the safety analysis. The incidence of TEAEs will be summarized by system organ class, preferred term, relationship to IP, and severity by treatment. Deaths, SAEs, and AEs leading to premature discontinuation will be listed. Vital signs, ECGs, physical examination data, and concomitant medications will also be summarized. Routine laboratory assessments will not be performed. Laboratory evaluations, if performed, will be listed.

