5.0 Analysis of Safety

The safety variables for this study are:

- Adverse events (AE)
- Vital signs (screening, Days 1-4)

- Physical examination (at screening only)
- Concomitant medications

Adverse Events

All AEs will be observed for each subject from enrollment until termination from the study. Prior to analysis, all AEs will be coded using MedDRA. Based on these coded terms, treatment emergent AEs (TEAEs) will be summarized using system organ class and preferred term by treatment and overall for all subjects in the safety population. This analysis will be repeated for serious TEAEs (TESAEs).

TEAEs will also be summarized by severity and relationship to IP. An overall summary table will provide the highest relationship and maximum severity observed per subject, as well as the counts of subjects with at least one TESAE.

All AEs will be listed, regardless of whether or not they were treatment emergent. AEs having an end date prior to signing the informed consent for this study will not be displayed in the AE data listings.

Vital Signs

Summary statistics (mean, median, sample size, standard deviation, minimum, and maximum) will be computed on the raw and change from baseline values for each vital sign parameter by time point, for each treatment. The screening time point will serve as baseline. If there are multiple vital signs taken at any time point, then the latest set of vital signs will be used for the analysis. All vital sign data will be listed.

Physical Exam

The physical exam data collected at screening will be listed.

Concomitant Medications

A table of the WHO-coded medications will be constructed by treatment group and overall with medications summarized by level 3 anatomical therapeutic chemical (ATC) term and Preferred Term. The number and percent of subjects on each drug will be summarized. A data listing for all concomitant medications will be provided.

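### Section 7.1 sets out to confirm tolerability, but a TEAE-only analysis of about 14 already-treated patients per arm over about 4 days can only describe it, and AEs present on Day 0 are summarised nowhere

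*Protocol*

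**What the plan says.** - **Objective.** The second bullet of Protocol 7.1, under the primary objectives, reads "To confirm the safety and tolerability of amifampridine phosphate by adverse event reports". It carries no rate, margin or hypothesis. The protocol synopsis and SAP 1.0 list only the efficacy co-primaries (QMG and SGI) as primary.
- **Population.** Inclusion criterion 1 (8.2.1) requires patients to be "currently receiving a stable dose of amifampridine phosphate for at least 7 days". Section 8.1 says that they come from open-label treatment in expanded access program EAP-001 and are then randomized 1:1 to drug or placebo through Day 4. About 28 patients are planned.
- **What is analysed.** Protocol 13.3: "Only TEAEs will be included in the safety analysis". SAP 5.0: "treatment emergent AEs (TEAEs) will be summarized using system organ class and preferred term by treatment and overall" (Tables 41 to 46 cover incidence, dose level, overall summary, serious events, relationship and severity). The analysis is descriptive.
- **AEs already present.** Protocol 9.1, on the expanded access log: "Any ongoing/open/unresolved AEs will be transcribed to the LMS-003 study AE Log". SAP 5.0: "All AEs will be listed, regardless of whether or not they were treatment emergent". That is Data Listing 8.
- **Worsening.** Protocol 9.1 includes among reportable AEs "Pre-existing medical conditions judged by the Investigator to have worsened in severity or frequency or changed in character during the study". It makes no exception for LEMS itself.

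**The concern.** The AE comparison is between staying on a drug and stopping it, in people who have already shown that they can take it. Three things follow for an objective about tolerability.

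First, patients who gave the drug up because of side effects cannot enter, so neither arm says anything about them.

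Second, a side effect present on Day 0 that simply continues on amifampridine is not a new or worsened event. Its disappearance on placebo is not an event either. Yet resolution against persistence is the one randomized tolerability contrast that this design can provide.

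Third, returning LEMS weakness on placebo meets the wording for a worsened pre-existing condition, so an effect of withdrawal may enter the safety tables as an adverse event of placebo.

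At stake is how the AE tables are read. Set beside a primary objective of confirmation, a similar or lower TEAE count on amifampridine could be taken as evidence about the drug's side-effect burden, when it partly reflects who was enrolled and what was stopped. The efficacy analyses are not affected.

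**Working it through.** The plan states no sample size, power or margin for safety, so there is no safety figure to reproduce. The check has three parts.

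**1. Where a Day 0 drug effect goes.** Neither document defines TEAE. Assume the usual meaning: onset or worsening after the first blinded dose.

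| Course from Day 0 to Day 4 | Tables 41 to 46 | Data Listing 8 |
|---|---|---|
| Persists unchanged on amifampridine | not counted | listed |
| Resolves on placebo | not counted | listed, with end date and outcome |
| Worsens in either arm | counted | listed |
| New in either arm | counted | listed |

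The first two rows are where the arms would differ if the drug causes lasting side effects, and no table summarises them. A definition anchored on the first open-label dose would instead count Day 0 effects in both arms alike, and would still not show resolution. The other safety data do not fill the gap: SAP 5.0 has the physical examination at screening only, and it uses screening, when patients are on drug, as the baseline for vital signs.

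**2. How withdrawal weakness could enter.** Let b be the proportion with an unrelated new AE, assumed equal in both arms. Let w be the proportion of placebo patients whose weakness is reported as an AE, assumed independent of b. Then:

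- TEAE incidence on amifampridine = b
- TEAE incidence on placebo = 1 − (1 − b)(1 − w)

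Neither b nor w is in the documents. With b = 10% as an illustration, amifampridine is at 10% and placebo is at:

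- w = 0: 1 − 0.90 × 1.00 = 10%
- w = 10%: 1 − 0.90 × 0.90 = 19%
- w = 30%: 1 − 0.90 × 0.70 = 37%
- w = 50%: 1 − 0.90 × 0.50 = 55%

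The gap therefore runs from 0 to 45 points, depending entirely on an unknown reporting habit. If the drug also produced new AEs, b would be higher on amifampridine and the gap would shrink or reverse. The prevalence of Day 0 drug effects appears in neither expression, so the TEAE comparison carries no information about it.

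**3. What the sample can exclude.** About 28 patients at 1:1 gives 28/2 = 14 per arm; the 26 in the sample-size section gives 13. After 0 events in n patients, the one-sided 95% upper bound is 1 − 0.05^(1/n):

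- n = 14: 1 − 0.05^(1/14) = 19.3%
- n = 13: 1 − 0.05^(1/13) = 20.6%

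For an 80% chance of seeing an event at least once in 14 patients, its true rate must be 1 − 0.20^(1/14) = 10.9%. These figures apply to about 4 days of blinded dosing in patients already selected for a stable dose.

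**The case against.** The strongest reply is that this is a second efficacy study (6.4.5). Its safety analysis is openly descriptive, it sits on a safety database of 1,455 people (6.4.3), and nothing in the plan says that fewer TEAEs will be claimed as better tolerability. Day 0 effects are not lost: they are transcribed, and Data Listing 8 shows treatment, start and end times, severity and outcome. With about 28 patients, a careful reader could reconstruct the contrast by hand. TEAEs are also tabulated by preferred term, so weakness coded to its own term would already have its own line.

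Most of this stands, and it limits the consequence. It does not rescue the wording: a descriptive analysis supports an objective to describe. A listing that could be tallied by hand is also not a planned summary.

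Several stronger readings are tempting and are not supported:

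- **That the TEAE tables must favour amifampridine whatever its tolerability.** New or worsened toxicity on drug does count. Whether weakness is entered as an AE is left to the investigator; 8.2.3 and SAP 2.3 deal with such worsening through early discontinuation and rescue and do not say whether it is an AE. The documents give no by-arm AE rates from a withdrawal study.
- **That the paresthesia rates in 6.4.1 measure Day 0 prevalence here.** They are incidences after single doses in healthy volunteers, and 6.4.3 describes such events as typically transient.
- **That the LEMS seizure proportion in 6.4.3 gives the expected yield here.** The trial excludes seizure disorder and active brain metastases (8.2.2), and exposure time behind that proportion is not given.

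**Conclusion.** The point holds in limited form. The plan cannot confirm safety and tolerability, because about 14 pre-selected patients on drug for about 4 days leave any unseen event type with an upper bound near 19% to 21%. It also leaves unsummarised the randomized comparison of resolution with persistence of existing drug effects. The second statement rests on the usual meaning of TEAE, which the plan should supply and does not.

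That withdrawal weakness could raise the placebo count follows from the AE definition in 9.1. Whether it would, and by how much, cannot be established from the documents, and the 0 to 45 point range above is illustration only. This is a worthwhile, inexpensive correction to the safety objective and its tables.

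**What to change.** 1. **Objective.** Reword the second bullet of 7.1 along these lines: *describe adverse events during 4 days of blinded continuation versus withdrawal in patients already on a stable dose*. Reconcile its primary status with the synopsis and SAP 1.0. State in 13.3 and SAP 5.0 that differences in TEAEs between arms reflect continuation versus withdrawal.
2. **One new SAP table.** Show AEs ongoing at Day 0, including those transcribed from EAP-001, by arm and preferred term, with the number resolved, unchanged or worsened by Day 4.
3. **Definitions.** Define TEAE in both documents, including how an intermittent effect that recurs after each dose is recorded. Flag LEMS-worsening events so that TEAE totals can be shown with and without them; preferred-term rows alone do not give those totals.

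The cost is some wording, one flag and one extra table. Section 9.1 already requires resolution dates, and Data Listing 8 already carries start, end and outcome, so no new visit or assessment is needed. The downside is a safety objective that sounds less favourable.

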8 INVESTIGATIONAL PLAN

[figure not shown]
8.1 Overall Study Design and Plan

This randomized (1:1), double-blind, placebo-controlled, parallel-group study is designed to evaluate the efficacy and safety of amifampridine phosphate in patients diagnosed with LEMS. Patients will have been receiving unblinded drug treatment in the expanded access program (EAP-001), after which blinded treatment effect will be assessed for continuation or cessation of drug. The study is planned to include approximately 28 male and female patients. The planned duration of participation for each patient is 5 days, excluding the screening period, which can last up to 7 days.

Those patients successfully satisfying all screening criteria will be randomized to a treatment group. Amifampridine phosphate (at the patient's optimal dose) or placebo will be dispensed by the site pharmacist, according to the randomization schedule, to begin with the next dose after all Day 0 assessments are completed and continued for 4 days. After completion of the study, patients will be eligible for expanded access treatment program with open-label amifampridine phosphate. Since patients will have been out of the expanded accesss program for less than 30 days, as LMS-003 participants, rescreening to return to expanded access program will not be required, per the protocol, and patients may immediately resume their participation in the expanded access program (EAP-001).

Page 29

Screening

Patients receiving amifampridine phosphate treatment for LEMS, and meeting the inclusion and exclusion criteria are eligible to participate in this study. They can be randomized if on stable dose and frequency of amifampridine phosphate for at least 1 week before being randomized to a treatment. Screening and randomization (Day 0) may be combined into a single visit.

Treatment (Days 1-4) (+1 day)

Patients will be randomized (1:1 ratio) on the last day of the screening period (Day 0) to either amifampridine phosphate or placebo. Beginning with the next dose after all Day 0 assessments are completed, the patient will take, under double-blind conditions, either amifampridine phosphate tablets or placebo tablets through Day 4, with a clinic visit on the last day (Day 4) for assessments (Table 3). Any unused portion of dispensed drug will be returned to the pharmacy.

During the study, safety and efficacy assessments will be made as detailed in the Schedule of Assessments in Table 3.

Table 3. Schedule of Assessments

	Samaaning	Randomization	Days 1-4
Study Assessment or Event	Screening Days -7 to -1	Day 0	Day 4 (+1 d)
Informed consent	X		
Inclusion/exclusion criteria	X		
Randomization		X	
Medical history	X		
Physical exam	X		
Vital signs	X		X
'Liquid biopsy' blood sample ¹	X		
Urine sample for amifampridine level ²			X
Pregnancy test – urine ³	X		
Blinded IP dispense		X	
IP accountability			X
CGI-I			X
SGI		X	X
QMG		X	X
3TUG		X	X
Patient most bothersome symptom question		X	X
Concomitant medications	X	X	X
Adverse Events	X	X	X

¹Optional test, at patient's discretion

²Urine specimen for amifampridine level will be collected on Days 3 and 4

³Women of child-bearing potential

Page 31

8.2 Selection of Study Population

Criteria for participation in the study are provided in Sections 8.2.1 and 8.2.2.

8.2.1 Inclusion Criteria

Individuals eligible to participate in this study must meet all of the following inclusion criteria:

- 1. Male or female ≥18 years of agewith LEMS and currently receiving a stable dose of amifampridine phosphate for at least 7 days.
- 2. Diagnosis of LEMS by antibody testing or EMG.
- 3. Completion of anti-cancer treatment at least 3 months (90 days) prior to Screening.
- 4. If receiving peripherally acting cholinesterase inhibitors (e.g. pyridostigmine), a stable dose of cholinesterase inhibitors is required for at least 7 days prior to randomization and throughout the study.
- 5. If receiving permitted oral immunosuppressants (prednisone or other corticosteroid,), a stable dose is required for at least 30 days prior to randomization and throughout the study.
- 6. Female patients of childbearing potential must practice effective, reliable contraceptive regimen during the study.
- 7. Able to perform all study procedures and assessments.
- 8. Willing and able to travel to study site and attend all clinic study visits.
- 9. Willing and able to provide written informed consent.

